Appendix 1 Schedule of Assessments (cont.)

		Treatment Visits															
Week	0 ^a	4	8	12	16 ^b	20 ^b	24	28 ^b	32 ^b	36	40 b	44 ^b	48 ^b	52	SC/		
		28	56	84	112	140	168	196	224	252	280	308	336	365	SFU d		
Day (±days)	1 ^c	(±4)	(±4)	(± 4)	(±3)	(±3)	(±7)	(±7)	(±7)	(±7)	(± 7)	(±7)	(±7)	(±7)	(±7)	ET	UV ^e
PAXgene RNA blood	X ⁹ , x			X x										Х	x		
Optional blood sample for genotyping ^y	х																

ACR=American College of Rheumatology; CCP=cyclic citrullinated protein; CRP=C-reactive protein; DAS=DAS=Disease Activity Score; eCRF=Electronic Case Report Form; ESR= erythrocyte sedimentation rate; ET=early termination; HAQ-DI= Health Assessment Questionnaire—Disability Index; OLE=open-label extension; PD=pharmacodynamics; PK=pharmacokinetic; PPI=proton pump inhibitor; SC=study completion; SFU=safety follow-up; TBNK=T, B, and natural killer cells; UV=unscheduled visit; VAS=visual analog scale.

- ^a Day 1 OLE assessments that overlap with Day 84 assessments in the main Study GA29350 do not need to be repeated.
- ^b This clinical visit is required only for women of childbearing potential for their monthly urine pregnancy testing.
- ^c Day 1 of Study GA30067 should be Day 84 in the blinded Study GA29350.
- ^d Safety follow-up should occur 8 weeks (±7 days) after last dose.
- An unscheduled visit represents a visit that is not as per Schedule of Assessments and is required for an adverse event or for potential relapse assessment. All indicated assessments do NOT need to be performed at each unscheduled visit. Assessments should be based on the reason for the unscheduled visit. These assessments may include collection of PK and PD, to assess drug exposure and/or PD measures of drug activity. Assessments performed during unscheduled visits should be recorded on the corresponding eCRF(s).
- f Patients who wish to enroll in this OLE study must complete up to Day 84 of Study GA29350 (but should not take blinded study drug on Day 84) prior to signing OLE Informed Consent Form.
- ⁹ Day 84 assessments in Study GA29350 should be used as the Day 1 assessments of Study GA30067.
- h Includes pulse rate, systolic and diastolic blood pressures while the patient is in a seated position, and temperature.
- Includes evaluation of the head, eyes, ears, nose, and throat and the cardiovascular, dermatological, musculoskeletal, respiratory, gastrointestinal, genitourinary, and neurological systems. Record abnormalities observed at baseline on the General Medical History and Baseline Conditions eCRF. At subsequent visits, record new or worsened clinically significant abnormalities on the Adverse Event eCRF.
- Perform a limited, symptom-directed examination at specified timepoints or as clinically indicated. Record new or worsened clinically significant abnormalities on the Adverse Event eCRF.

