2. OBJECTIVES AND ENDPOINTS

This OLE study will evaluate the long-term safety and efficacy of GDC-0853 in patients with RA. Specific objectives and corresponding endpoints and analyses for the study are outlined in Table 1.

Table 1 Primary (Safety), Efficacy, Pharmacokinetic, and Exploratory Objectives with Corresponding Endpoints

Objectives	Corresponding Endpoint(s)	
Primary Objective (Safety)		
To evaluate the long-term safety of GDC-0853 over an extended treatment period of up to 52 weeks	 The nature, frequency, severity, and timing of adverse events Changes in vital signs, physical findings, ECGs, and clinical laboratory results during and following GDC-0853 administration 	
Primary Efficacy Objective		
 To evaluate the efficacy of GDC-0853 (analyzed separately for MTX-IR and TNF-IR patients) at Week 52 relative to baseline in Study GA29350 	ACR50 response at Week 52	
Secondary Efficacy Objective		
 To determine the improvement in disease activity through 52 weeks of treatment (analyzed separately for MTX-IR and TNF-IR patients) relative to baseline in Study GA29350 	 ACR50 response up to Week 12 ACR20, ACR70, DAS 28-3 (CRP), DAS 28-4 (CRP), DAS 28-3 (ESR), and DAS 28-4 (ESR) response up to Week 52 	
• To assess DAS28 remission (<2.6) and LDA (<3.2) state	States up to Week 52	
• To assess ACR/EULAR remission according to the Boolean-based definition (tender joint count ≤1, swollen joint count ≤1, CRP ≤1, and patient global assessment ≤1)	Remission status up to Week 52	
• To assess SDAI-based remission (defined as ≤3.3 for ACR/EULAR remission) and CDAI-based remission	Remission status up to Week 52	
To assess efficacy based on the individual components of the ACR relative to baseline in Study GA29350	Response status up to Week 52 for: Tender/Painful Joint Count (68) Swollen Joint Count (66) Patient's Assessment of Arthritis Pain Patient's Global Assessment of Arthritis Physician's Global Assessment of Arthritis CRP HAQ-DI	

Objectives	Corresponding Endpoint(s)	
To evaluate the effect of GDC-0853 on health-related quality of life	SF-36, standard, Version 2, questionnaire through 52 weeks	
To evaluate the effect of GDC-0853 on fatigue	FACIT-Fatigue Scale up to Week 52	
Pharmacokinetic Objectives		
To characterize the pharmacokinetics of GDC-0853 in patients using a population PK approach	Steady-state PK parameters (AUC _{0-t} , C _{trough} , t _{1/2} , apparent CL/F)	
Exploratory Pharmacokinetic Objectives:		

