5.1.1.5 Gastrointestinal Effects

Body weight gain and food consumption changes have been observed in animals, including nonsignificant increases in male Wistar-Han rats administered ≥ 2 mg/kg/day (4.3 $\mu M \bullet h$) for 6 months, and significant reductions in rats administered 100 mg/kg/day (1438 $\mu M \bullet h$) and dogs administered 25 mg/kg (180 $\mu M \bullet h$) for 4 weeks. These effects on body weight gain and food consumption were reversible following discontinuation of GDC-0853 dosing.

Grade 1 diarrhea, nausea, and abdominal pain have been reported in in patients with B-cell malignancies; however, the events have resolved and have not led to study drug discontinuation. Healthy subjects in the MAD Study GA29347 reported events of mild self-limited nausea.

Throughout the study, patients will be monitored for GI effects.

Guidelines for management GDC-0853 in the event of GI side effects in patients are provided in Table 3. Please refer to the GDC-0853 Investigator's Brochure for further details.

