6. STATISTICAL CONSIDERATIONS AND ANALYSIS PLAN

Because of the non-comparative nature of the study, no statistical tests are planned. All efficacy parameters will be summarized descriptively. Demographic and baseline characteristics will be summarized descriptively.

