6.1 DETERMINATION OF SAMPLE SIZE

No formal sample size calculations were performed for this OLE study. The maximum number of patients eligible for enrollment is approximately 580 (i.e., all patients enrolled in Study GA29350).

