Appendix 1 Schedule of Assessments (cont.)

- Triplicate digital ECG recordings will be obtained at weeks 0 (collected on Day 84 of Study GA29350), 4, 8 and 12, single ECG recording otherwise. The ECG intervals (e.g., PR, QRS, QT, QTcF, and RR) and heart rate will be entered into the eCRF; in addition, ECG readings will be stored for future analysis, if needed. ECGs for each patient should be obtained from the same machine whenever possible. To minimize variability, it is important that patients be in a resting position for ≥10 minutes prior to each ECG evaluation. Body position should be consistently maintained for each ECG evaluation to prevent changes in HR. Environmental distractions (e.g., television, radio, conversation) should be avoided during the pre-ECG resting period and during ECG recording.
- Patients will receive oral GDC-0853 200 mg twice daily (unless dose reduction is indicated) approximately every 12 hours starting on Day 1 (starting with the a.m. dose) and ending on Day 365 (52 weeks). GDC-0853 should be taken with water by mouth. The dates and times of the most recent prior meal, last dose of oral study drug (prior to clinic visit), and timing of study drug administration in clinic should be recorded at each clinic visit. At the indicated clinic visits during the first 12 weeks of the study, patients should be instructed that the first (a.m.) dose of GDC-0853 will be administered in the clinic. After Week 12, GDC-0853 administration in the clinic is not required.
- ^m The last dose of blinded study drug in Study GA29350 is the p.m. dose on the day before the Week 12 (Day 84) visit for all patients. For patients continuing into the OLE Study GA30067, the first open label dose of GDC-0853 should be the a.m. dose on Day 84 (which is Day 1 of Study GA30067).
- ⁿ Includes WBC count, RBC count, hemoglobin, hematocrit, platelet count, differential count (neutrophils, eosinophils, basophils, monocytes, lymphocytes, other cells).
- ° Includes sodium, potassium, chloride, bicarbonate, glucose, BUN or urea, creatinine, total protein, albumin, phosphorus, calcium, total and direct bilirubin, ALP, ALT, AST, uric acid, LDH, lipase and amylase
- ^p During this study, monthly urine pregnancy testing is required for women of childbearing potential. Tests will be performed locally at specified clinic visits. If a urine pregnancy test result is positive, it must be confirmed by a serum pregnancy test (performed locally).

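### In patients who complete 52 weeks, Appendix 1 schedules no on-treatment weight after Day 1 and no on-treatment lipid panel or RF/anti-CCP after Week 12

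*Combined protocol and SAP*

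**What the plan says.** Table 1 (Section 2) gives the primary objective as "To evaluate the long-term safety of GDC-0853 over an extended treatment period of up to 52 weeks". One of its two endpoints is "Changes in vital signs, physical findings, ECGs, and clinical laboratory results during and following GDC-0853 administration". Section 6.4 analyses safety from adverse events, laboratory results and vital signs. Section 6 is descriptive throughout: "Because of the non-comparative nature of the study, no statistical tests are planned".

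Appendix 1 gives Week 52 (Day 365) and SC/SFU separate columns. The abbreviations read "SC=study completion; SFU=safety follow-up", and footnote d fixes the timing of the second column: "Safety follow-up should occur 8 weeks (±7 days) after last dose". Section 3.1 likewise places the follow-up visit after the 52-week treatment period.

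Weight, the lipid panel and RF/anti-CCP carry an SC/SFU mark but no Week 52 mark. Section 4.4.7 lists lipids and rheumatoid factor/anti-CCP as central-laboratory tests. Section 5.1.1.5 reports weight and food-consumption changes in animals and adds: "These effects on body weight gain and food consumption were reversible following discontinuation of GDC-0853 dosing".

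**The concern.** An extension study with a long-term safety objective should yield at least one reading of each scheduled safety measure near the end of treatment. For these three measures the end-of-study reading in completers is taken after about 8 weeks without drug. It can speak to the period following administration but not to the end of the dosing period. Completers carry most of the long-term information, and a measurement that was not taken cannot be recovered at analysis.

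The omission looks unintended. Hematology, chemistry, urinalysis, TBNK, CRP, ESR, SF-36, FACIT-Fatigue and the serum and plasma biomarkers are all marked at both Week 52 and SC/SFU, which gives an on-drug and an off-drug reading. These three rows have only the off-drug half, and no reason is stated.

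**Working it through.** There is no sample-size or power figure to reproduce: "No formal sample size calculations were performed for this OLE study". The check is a reading of the schedule followed by date arithmetic.

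**Step 1: read the rows.** Appendix 1 has 17 columns: 14 weeks from 0 to 52, then SC/SFU, ET and unscheduled visit (UV). The three rows in question each resolve into 17 cells. So do hematology, quantitative Ig and TBNK, which show a Week 52 mark, so the columns are aligned.

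| Row | Marked at | Scheduled on-treatment values after Day 1, completer |
|---|---|---|
| Weight | Week 0, SC/SFU, ET | 0 |
| Lipid panel | Week 12, SC/SFU, ET | 1 (Week 12) |
| RF/anti-CCP | Week 12, SC/SFU | 1 (Week 12) |
| Hematology, for comparison | Weeks 0, 4, 8, 12, 24, 36, 52, SC/SFU, UV | 6 |
| Quantitative Ig, for comparison | Weeks 0, 12, 24, 36, 52, UV | 4 |
| TBNK, for comparison | Weeks 0, 12, 24, 52, SC/SFU, ET, UV | 3 |

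**Step 2: look for the values elsewhere.**

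- Vital signs (Section 4.4.4) are pulse, blood pressure and temperature, without weight.
- The chemistry panel (Section 4.4.7) does not include lipids.
- Physical examinations after Day 1 are limited and symptom-directed (Section 4.4.3).
- The ET visit for stopping treatment applies before the Week 52 visit (Section 4.5.1), so completers do not have it.
- None of the three rows is marked at UV.

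No other section supplies a Week 52 value.

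**Step 3: timing in a completer.**

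- Last dose: Day 365 (dosing footnote, Appendix 1).
- SC/SFU: 365 + 56 = Day 421, with a window of Day 414 to Day 428. That is about Week 60 and agrees with the stated 52 + 8 = 60 weeks.
- Time off drug at that reading: 56 days (49 to 63).
- Lipids and RF/anti-CCP, treatment time after the last on-drug value: 365 − 84 = 281 days, or 52 − 12 = 40 weeks; 40/52 = 77%.
- Interval from Week 12 to the next value: 421 − 84 = 337 days.
- Weight: every treatment week after Day 1 is unobserved.

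**Step 4: the starting point.** Week 0 is Day 84 of Study GA29350 (footnotes c and g). Section 1.3 describes GDC-0853, placebo and adalimumab arms in that study. For patients from GDC-0853 arms, the Week 0 weight follows 12 weeks of that drug, so Week 0 to SC/SFU runs from on drug to off drug. For the others it runs from before GDC-0853 to after it. Lipids and RF/anti-CCP have no Week 0 mark. Section 4.4 says only that parent Day 84 laboratory tests serve as baseline, without naming these two.

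**The case against.** The strongest reply is that little rides on these rows. Section 5.1.1 names no lipid or autoantibody risk, and neither is an adverse event of special interest. RF/anti-CCP is in no objective or endpoint in Table 1. Weight is not a vital sign and is not named in the primary endpoint or in Section 6.4. Clinically significant findings are recorded as adverse events in any case. After Week 12, methotrexate, other DMARDs and corticosteroids may change, so a Week 52 shift in weight or lipids in a single-arm study could not readily be attributed to GDC-0853. Much of this stands: it limits the importance of RF/anti-CCP and keeps any Week 52 result descriptive. It does not close the gap. Lipids are clinical laboratory results within the primary endpoint, and a laboratory abnormality cannot be reported as an adverse event if the test is not done.

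A reader might also infer three stronger things that the documents do not support.

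- *That last values are confounded with early stopping*, because early stoppers are measured at ET and completers off drug. Sections 4.5.1 and 4.5.2 send early stoppers to the 8-week follow-up as well, so the planned last visit is off drug in both groups. The mismatch arises only if ET and SC/SFU values are pooled. Nor is ET always on drug: Section 4.5.1 also uses it for patients who leave during follow-up.
- *That a weight effect is expected at the clinical exposure.* The finding at 4.3 µM·h was a nonsignificant increase in male rats. The significant reductions were at 180 µM·h in dogs and 1438 µM·h in rats. Section 3.3.1 expects mean exposure below 10 µM·h, and 180/10 = 18 times that ceiling. The protocol predicts no weight effect in patients.
- *That the result is biased toward no effect.* Under an assumed exponential reversal with a half-time of 1 to 3 weeks, the share remaining after 8 weeks would be 2^−(8/1) = 0.4% to 2^−(8/3) = 16%. That half-time has no source in the documents, and a slower one would leave more. Section 5.1.1.5 says the animal changes reversed but gives no time. The mixed starting point at Week 0 leaves the direction open too.

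**Conclusion.** The gap is real. In completers the schedule gives no on-treatment weight after Day 1 and a single on-treatment lipid and RF/anti-CCP value at Week 12, leaving 40 of 52 treatment weeks unobserved for the latter two. The next value is about 56 days off drug. The plan therefore cannot describe change in these measures during long-term dosing, although its primary endpoint covers that period and most other laboratory rows are marked at Week 52. Lipids have the strongest claim, then weight; RF/anti-CCP has the weakest.

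This rests on the Appendix 1 marks as printed and on a last dose at Day 365. It needs no assumption about how fast an effect reverses. It does not establish that any conclusion is biased, or by how much. It is a modest scheduling omission worth correcting, because the missing data cannot be recovered later.

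**What to change.** In Appendix 1, mark weight, lipid panel and RF/anti-CCP at Week 52, and keep their SC/SFU marks as the off-drug reading. Add the Week 52 marks rather than moving the existing ones: moving would lose the value that serves the post-administration part of the endpoint.

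In the analysis plan, summarise Week 52 (or ET, where that visit falls at the end of treatment) as the end-of-treatment value, separately from SC/SFU. Do not pool them as a last observation.

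The cost per completer is one weighing plus a lipid panel, RF and anti-CCP on blood already drawn at Week 52, in a study of at most about 580 patients. The added values remain descriptive, since concomitant therapy may change after Week 12.

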Appendix 1 Schedule of Assessments (cont.)

- Triplicate digital ECG recordings will be obtained at weeks 0 (collected on Day 84 of Study GA29350), 4, 8 and 12, single ECG recording otherwise. The ECG intervals (e.g., PR, QRS, QT, QTcF, and RR) and heart rate will be entered into the eCRF; in addition, ECG readings will be stored for future analysis, if needed. ECGs for each patient should be obtained from the same machine whenever possible. To minimize variability, it is important that patients be in a resting position for ≥10 minutes prior to each ECG evaluation. Body position should be consistently maintained for each ECG evaluation to prevent changes in HR. Environmental distractions (e.g., television, radio, conversation) should be avoided during the pre-ECG resting period and during ECG recording.
- Patients will receive oral GDC-0853 200 mg twice daily (unless dose reduction is indicated) approximately every 12 hours starting on Day 1 (starting with the a.m. dose) and ending on Day 365 (52 weeks). GDC-0853 should be taken with water by mouth. The dates and times of the most recent prior meal, last dose of oral study drug (prior to clinic visit), and timing of study drug administration in clinic should be recorded at each clinic visit. At the indicated clinic visits during the first 12 weeks of the study, patients should be instructed that the first (a.m.) dose of GDC-0853 will be administered in the clinic. After Week 12, GDC-0853 administration in the clinic is not required.
- ^m The last dose of blinded study drug in Study GA29350 is the p.m. dose on the day before the Week 12 (Day 84) visit for all patients. For patients continuing into the OLE Study GA30067, the first open label dose of GDC-0853 should be the a.m. dose on Day 84 (which is Day 1 of Study GA30067).
- ⁿ Includes WBC count, RBC count, hemoglobin, hematocrit, platelet count, differential count (neutrophils, eosinophils, basophils, monocytes, lymphocytes, other cells).
- ° Includes sodium, potassium, chloride, bicarbonate, glucose, BUN or urea, creatinine, total protein, albumin, phosphorus, calcium, total and direct bilirubin, ALP, ALT, AST, uric acid, LDH, lipase and amylase
- ^p During this study, monthly urine pregnancy testing is required for women of childbearing potential. Tests will be performed locally at specified clinic visits. If a urine pregnancy test result is positive, it must be confirmed by a serum pregnancy test (performed locally).
- ^q Includes dipstick (pH, specific gravity, glucose, protein, ketones, blood) and microscopic examination (sediment, RBCs, WBCs, casts, crystals, epithelial cells, bacteria).
- ^r Includes IgM, IgA, IgG, and IgE.
- ^s Fasting sample not necessary.
- t Tender and Swollen Joint Count improvement should be calculated at Week 12 and 24 of OLE with use of formula provided in Appendix 9.
- ^u Questionnaires will be self-administered before the patient receives any information on disease status, prior to the performance of non-PRO assessments, and prior to the administration of study treatment.
- ^v The same clinician should complete the Physician's Global Assessment of Arthritis throughout the study.
- ^u Collect prior to drug administration. Blood for PBMCs will be shipped overnight to central laboratory for processing.

Appendix 1 Schedule of Assessments (cont.)

- The dates and times of the most recent prior meal and most recent prior dose of PPI, H2-RA, or other antacid (e.g., Maalox®, Pepto-Bismol®, Rolaids®) last dose of oral study drug (prior to clinic visit), and timing of study drug administration in clinic (on Days 1 and 84) should be recorded at clinic visits at which PK samples are collected.
- ^w Collect prior to drug administration. Blood for flow cytometry analysis (e.g., B cell and monocyte subsets). To be performed at select centers in the United States where samples can be shipped to FACS laboratory within 24 hours.
- ^x Sample to be collected prior to drug administration.
- Not applicable if optional WGS sample was collected in Study GA29350. WGS is contingent upon the review and approval by each site's IRB/EC and, if applicable, an appropriate regulatory body. If a site has not been granted approval for WGS, this assessment will not be applicable at that site. A single blood sample will be collected for WGS and may be sent to one or more laboratories for analysis.

Appropriate Equivalent Morphine Doses of Opioid Analgesics Common Opioid Analgesics

Drug	Maximum Allowed Total Daily Dose	Relative Potency to Oral Morphine	Half-Life
Morphine	30 mg	1	1.5-4 hours
Hydrocodone (Vicodin, Lortab)	30 mg	1	3.8–4.5 hours
Hydromorphone (Dilaudid)	7.5 mg	4	2.5 hours
Meperidine (Demerol, Pethidine)	300 mg	0.1	3.2–3.7 hours
Methadone (Dolophine, Methadose, Physeptone)	10 mg	3.0	23 hours
Codeine (Paveral, Tylenol #2 and #3)	200 mg	0.15	2.5–3.5 hours
Oxycodone [Roxicodone; Percocet, Tylox]	15 mg	~2	3.2 hours
Tramadol [Ultram, Zydol; Zamadol, Ultracet, Tramal]	300 mg	~0.1	4.7–5.1 hours
Propoxyphene HCI (Darvon, Darvocet, Doloxene)	300 mg propoxyphene HCl	~0.1	6–12 hours; 30–36 hours for
Propoxyphene napsylate (Darvon-N, Darvocet-N 100)	400 mg propoxyphene napsylate		active metabolite (norpropoxyphene)

Note: Sites should contact the project team for acceptable alternative preparations and related data.

Appendix 3 Concomitant Medications (Including Foods and Herbal Products)

Class	Expected Interaction	Recommendation	Examples of Drugs in this Class ^a			
Antacids	Decreased GDC-0853 absorption due to increased gastric pH	Take GDC-0853 2 hours before or 2 hours after antacid	Maalox®, Pepto-Bismol®, Rolaids®			
Moderate or strong CYP3A inhibitors	Increased GDC-0853 plasma concentrations due to inhibition of metabolism	Avoid for 7 days or 5 half-lives (whichever is longer) prior to first dose of study drug and during the treatment period	 Antimicrobials (clarithromycin, erythromycin, itraconazole, ketoconazole, telithromycin, troleandamycin, voriconazole, posaconazole) Antidepressants (nefazodone) Antihypertensive/cardiac (verapamil, diltiazem) Other (grapefruit juice, Seville orange juice, pomegranate, star fruit) 			
CYP3A inducers	Decreased GDC-0853 plasma concentrations due to increased metabolism	Avoid for 7 days or 5 half-lives (whichever is longer) prior to first dose of study drug and during the treatment period	 Antimicrobials (rifampin, rifapentine, rifabutin) Antidepressants (St. John's wort, hyperforin) Antiepileptics (carbamazepine, phenytoin, phenobarbital, hyperforin) Diabetes (pioglitazone, troglitazone) Other (modafinil, bosentan) 			

